### **20.3 Confidentiality and HIPAA/GDPR Compliance**

Participant confidentiality is strictly held in trust by the Site PIs and study personnel. This confidentiality is extended to cover testing of biological samples and genetic tests in addition to the clinical information relating to participants. Some of the data collected as part of this protocol is of potential medical relevance including cognitive and neuropsychological testing, brain MRI, PET, and genetic testing. These are all tests that can be obtained as part of routine medical care for patients with symptoms suspected as being due to Alzheimer's disease, and are being collected in this study using clinically standard methods. The results of these tests may be disclosed to our study participants and their study partners.

Due to the clinical relevance, the MRI report (or summary of the findings), summary of the cognitive testing, clinical diagnosis and summary of PET results (CI cohorts only) can be placed in medical records by the study team or the participant. Participants will be informed of this in the informed consent. Since genetic testing results are sensitive information, participants will be explicitly asked for permission to place genetic results from LEADS in their medical record. In the rare occasion where the institutional policies require that all genetic testing results are part of the medical record, the participant will be informed and have the option to opt out of participation in LEADS.

Authorized representatives of the sponsoring institution may inspect all research documents and records required to be maintained by the Site PI, as well as medical records (office, clinic or hospital) and pharmacy records for the participants in this study. The enrolling study site will permit access to such records. Any data, specimens, forms, reports, and other records that leave the site will be identified only by a participant identification number (Participant ID, PID) to maintain confidentiality. All records will be kept in a locked file cabinet. All computer entry and networking programs will be done using PIDs only. Information will not be released without written permission of the participant, except as necessary for monitoring by IRB/IEC, the FDA, the NIA, and the OHRP.

Information about U.S. study participants will be kept confidential and managed according to the requirements of the Health Insurance Portability and Accountability Act of 1996 (HIPAA). Those regulations require a signed participant HIPAA Authorization informing the participant of the following:

- What PHI will be collected from participants in this study
- Who will have access to that information and why
- Who will use or disclose that information
- The rights of a research participant to revoke their authorization for use of their PHI.

In the event that a U.S. participant revokes authorization to collect or use PHI, the Site PI, by regulation, retains the ability to use all information collected prior to the revocation of participant authorization. Each Site PI, under the guidance of the IRB, is responsible for

ensuring that all applicable HIPAA regulations and State laws are met. International Site PIs, under the guidance of their IRB are responsible for ensuring that all applicable local regulations are met.

Information about international study participants will be kept confidential and managed according to the requirements of the General Data Protection Regulation (GDPR), or their local regulations.

In the event that an international participant revokes authorization to collect or use PHI, the Site PI, by regulation, retains the ability to use all information collected prior to the revocation of participant authorization. Each international Site PI, under the guidance of their local regulatory body is responsible for ensuring that all applicable GDPR regulations and/or local laws are met.

## **20.4 Certificate of Confidentiality**

To further protect the privacy of study participants, a Certificate of Confidentiality has been automatically issued by the NIH to protect identifiable research information from forced disclosure. It allows the Site PI and others who have access to research records to refuse to disclose identifying information on research participation in any civil, criminal, administrative, legislative, or other proceeding, whether at the federal, state, or local level. By protecting researchers and institutions from being compelled to disclose information that would identify research participants, Certificates of Confidentiality help achieve the research objectives and promote participation in studies by helping assure confidentiality and privacy to participants.

# **21.0 STATISTICAL CONSIDERATIONS**

## **21.1 Analysis Goals and Strategies**

The Biostatistics Core will conduct interim and final analyses of the clinical, imaging and genomic data for the hypotheses and aims of the study. The goals of the analyses are briefly described below.

### **21.1.2 Statistical analysis**

The analysis of the data will focus on comparing the cognitive and biomarker measures between LEADS EOAD and LEADS CN and LEADS EOAD and ADNI LOAD participants. We will also compare *APOE4*+ and non-carriers within and between diagnostic groups (EOAD, CN, and LOAD). We will study the associations between our cognitive composite scores and imaging and other biomarkers. Longitudinal analyses will be conducted to identify differences of longitudinal changes in cognitive, imaging and fluid biomarker measures between LEADS EOAD and ADNI LOAD participants and between *APOE4*+ and non-carriers within and between diagnostic groups (EOAD and LOAD). Finally, we will perform exploratory analysis of EOnonAD patient data.

#### ***Aim 1***

Baseline composite cognitive scores will be developed using clustering techniques such as kNN clustering. The cognitive data will be collected in integer scales for each test. Differences of the composite scores within cognitive domains between

LEADS EOAD and ADNI LOAD participants will be assessed using multivariate linear regression controlling for the effects of candidate confounders such as education and sex. The results will be presented using graphical methods and tables of statistical summary estimates and test results. Longitudinal changes in cognitive scores will be assessed using linear mixed models and machine learning approaches.

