The study will also leverage existing data. We plan to compare our EOAD individuals to ADNI LOAD participants. ADNI is a non-randomized, natural history, non-treatment study with up to 2000 longitudinal LOAD participants with clinical, cognitive, MRI, amyloid and tau PET, CSF and peripheral blood data collected across approximately 59 sites in the United States and Canada. ADNI data is freely shared with other researchers.

In addition, all of our sites who are federally funded Alzheimer’s Disease Research Centers under the auspices of the National Alzheimer Coordinating Center (NACC) will be encouraged to enroll all subjects in their longitudinal observational clinical cohorts. We will leverage the ADRCs as they are well positioned to follow their research participants indefinitely (until death) and are also funded to perform post mortem examinations of the brain tissue. This partnership will greatly benefit the LEADS program as it will secure a mechanism for longitudinal follow-up. A portion of the standardized NACC assessment will be adopted into the LEADS study.

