## 4.0 STUDY DESIGN AND INVESTIGATIONAL PLAN

The LEADS design builds on the success of two major natural history/biomarker initiatives in AD: ADNI and DIAN. Like those initiatives, the LEADS approach links longitudinal clinical and cognitive assessments with multiple imaging and biofluid markers that capture different elements of the AD pathophysiological cascade. Its alignment to ADNI will allow us to use ADNI LOAD participants as a disease comparison group.

LEADS is a non-randomized, natural history, non-treatment study. Approximately 850 cognitively impaired (EOAD and EOnonAD) participants and 100 CN participants will be enrolled at approximately 20 sites in the United States. Approximately 40 CI participants and 10 CN participants will be enrolled in sites outside of the U.S. as a part of iLEADS, the international expansion of LEADS. Clinical/cognitive, imaging, biomarker, and genetic characteristics will be assessed across the three cohorts: EOAD, EOnonAD, and CN.

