## 13.0 SITE QUALIFICATIONS

Participants will be enrolled at approximately 25 clinical sites in the United States and abroad. All of these sites have significant experience with diagnosing and treating patients with EOAD and have agreed to participate in the study.

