## 15.2 MRI and PET Imaging Data Storage

LONI at the University of Southern California (USC) was selected to leverage the pre-existing infrastructure for imaging and clinical data storage. MRI and PET data will be transmitted by enrolling sites directly to LONI. All scans will be labeled using LEADS participant identifiers and scanner specific series descriptions. All scans will undergo a de-identification process, which is embedded within the LONI upload process to ensure that no direct participant identifier information is present in the image files.

- **MRI Images:** Images will be uploaded by sites directly to LONI. PHI will be limited to the minimum necessary for authorized oversight and placed into quarantine until they pass quality assurance evaluation conducted by the MRI Core. The MRI Core will perform a quality control review on each MRI scan. Quality control for MRI will result in failure of some scans, which may need to be repeated. Repeat scans must be scheduled as soon as possible and no later than four weeks of the visit date. Repeat scans will not be considered protocol deviations.
- **PET Images:** Images are uploaded by site users to LONI. PHI will be limited to the minimum necessary for authorized oversight and placed into quarantine until they pass quality assurance evaluation conducted by the PET Core. The aim of this work is not only to make sure that all PET scans are acquired and reconstructed using the appropriate protocols and that image quality is good, but to standardize the images from the different sites (and hence the different PET scanner vendors and models) as much as possible in order to reduce inter-site differences. Quality control of scans could necessitate salvage with reprocessing of the raw imaging data. All sites are required to save original PET data for the duration of the study.

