#### **Aim 2**

MRI and PET based biomarker volumes computed at the mm^3 scale, will be used to assess baseline and longitudinal associations of composite cognitive scores and imaging metrics and identify differences between LEADS EOAD and ADNI LOAD participants. Specifically, multiple linear regression analysis will be used to identify differences between imaging-based metrics in LEADS EOAD vs. ADNI LOAD at baseline and to assess correlations between composite cognitive and imaging measures, while longitudinal data will be analyzed using mixed effects models when data for more than 2 visits per participant is collected. Relevant confounders (e.g. sex, education) will be included as covariates. In addition, summary MRI and PET measures will be analyzed using machine learning techniques to identify a composite metric capturing change across LEADS EOAD participants.

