### 21.1.4 Sample Size

Sample size considerations were developed for each aim and are presented below. The computations of sample size assumed a target power of 90% at significance level of 0.05. A total sample size of 650 EOAD participants is envisioned for the study. The specific effect sizes for each of the aims are presented below. In general, these effect sizes are smaller or equal to those observed in our preliminary data.

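### The baseline EOAD versus ADNI LOAD regressions make no allowance for clustering of participants within sites, so their standard errors would be too small if outcomes differ between sites

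*Protocol*

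**What the plan says.** Section 21.1.2, Aim 1: differences in domain composite scores between LEADS EOAD and ADNI LOAD "will be assessed using multivariate linear regression controlling for the effects of candidate confounders such as education and sex". Section 21.1.2, Aim 2: "multiple linear regression analysis will be used to identify differences between imaging-based metrics in LEADS EOAD vs. ADNI LOAD at baseline", again with sex and education given as example covariates. Under both aims, mixed models are named only for the longitudinal data.

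On sites, Section 4.0 says the US participants "will be enrolled at approximately 20 sites in the United States". Section 13.0 gives the total: "Participants will be enrolled at approximately 25 clinical sites in the United States and abroad". Section 1.0 describes ADNI data as coming from "approximately 59 sites in the United States and Canada", with up to 2000 LOAD participants. Section 15.2 says PET images from different sites are standardised as far as possible "in order to reduce inter-site differences".

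On size, Section 21.1.4 says: "The computations of sample size assumed a target power of 90% at significance level of 0.05" and "A total sample size of 650 EOAD participants is envisioned for the study". For Aim 1 it claims 90% power for a difference of -0.26 in composite Z-score. Section 21 does not mention site, an ICC or a cluster-adjusted standard error.

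**The concern.** Ordinary linear regression treats each participant as an independent observation. Here participants share a site, and with it a recruitment source (6.0), a consensus diagnosis panel (7.2), raters supervised by the site investigator (13.1) and usually a scanner. If any of this shifts scores or image metrics, participants at one site are correlated.

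The comparison also lies largely between sites. At most about 20 of the roughly 59 ADNI sites can be US LEADS sites, so if the LOAD sample is spread over all of ADNI, at least about 39 of its sites contribute no US EOAD participants and their effects cannot cancel.

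Education and sex, and other confounders added to that open list, enter the model for the mean. They do not give the estimate a variance that reflects correlation within site. Site as a fixed effect is no simple way out, because the EOAD-LOAD contrast would then be identified only from centres in both studies.

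H1a and the baseline part of H2a rest on these contrasts. At stake are intervals that are too narrow, p-values that are too small, and small differences due to site mix being reported as features of EOAD.

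**Working it through.** **Inputs from the protocol.** 650 EOAD; about 20 US LEADS sites (32.5 EOAD per site), about 25 in all; about 59 ADNI sites; alpha 0.05; 90% power; difference 0.26 Z.

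**Assumptions, because the protocol gives no figure.** Two-sided test; residual SD 1; equal site sizes; LOAD spread over all 59 ADNI sites; LOAD number nL of 204, 650 or 2000; 0 to 20 shared sites; site ICC of 0.01 to 0.10.

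**Step 1: the plan's own power figure.** Under independence, 90% power requires a variance of the difference of (0.26 / (1.960 + 1.282))² = 0.006434. Setting 1/650 + 1/nL equal to this gives nL of about 204. With 650 LOAD the power would be 99.7%, and with 2000 it would be 99.99%. The stated 90% can be neither confirmed nor refuted without the LOAD number and SD; 204 is the number consistent with it under SD 1.

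**Step 2: variance with clustering.** With total variance 1 and m shared sites:

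- Independent variance: V0 = 1/650 + 1/nL
- Clustered variance: V = ICC × S + (1 − ICC) × V0
- Site term: S = 1/20 + 1/59 − 2m/(20 × 59), which is 0.06695 for m = 0 and 0.03305 for m = 20
- Actual error of the nominal 5% test: 2 × (1 − Φ(1.96 / √(V/V0)))

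Worked case, ICC 0.05, nL = 204, m = 0: V0 = 0.006440; V = 0.05 × 0.06695 + 0.95 × 0.006440 = 0.009466; ratio 1.47; error 2 × (1 − Φ(1.96/1.212)) = 10.6%.

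**Step 3: range of error rates** (20 LEADS sites; all 20 shared to none shared).

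| ICC | 204 LOAD | 650 LOAD | 2000 LOAD |
|---|---|---|---|
| 0.01 | 5.5-6.1% | 6.1-7.5% | 6.8-8.8% |
| 0.02 | 6.0-7.2% | 7.3-9.9% | 8.6-12.6% |
| 0.05 | 7.4-10.6% | 10.8-17.0% | 14.0-22.3% |
| 0.10 | 9.9-15.9% | 16.3-26.4% | 21.7-33.8% |

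Spreading the 650 EOAD over 25 LEADS sites, with 20 to none shared, gives 7.1-9.7%, 10.2-15.2% and 13.1-20.1% at ICC 0.05.

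**Step 4: the case with no inflation.** If LOAD came from the same 20 sites in balance, S = 0, the variance ratio is 0.95 and the error is 4.4%.

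**Step 5: power with the clustered variance.** At 204 LOAD and ICC 0.05, power for 0.26 is Φ(0.26/√V − 1.96), which is 76% with no shared sites and 84% with all 20 shared, against 90%. At ICC 0.01 it is 87-89%. With 2000 LOAD at ICC 0.05 it stays at about 94% or more, so there the issue is false positives rather than power.

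**Step 6: does a site term repair it?** In simulation at ICC 0.05 (2000 runs per setting), the independent-observation test rejected a true null in 7.3-21.4% of runs. A model with a random site intercept rejected in 4.3-6.2%.

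**The case against.** The strongest objection is that this is detail for a statistical analysis plan, which is not at hand. Section 21.1 says it describes goals only briefly, the covariate lists are open, and no standard-error method is fixed, so cluster-robust standard errors would fit within the named regression. This stands in part: the protocol does not rule out a valid analysis, and it cannot be said that the standard errors will be wrong. But Section 21.1.2 does name a method, and it names mixed models for longitudinal data only. Followed as written, the baseline method has no allowance for clustering.

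A second objection is that every quantity driving the size comes from outside the documents. This stands, and is why ranges are shown. A reader might infer from the top of the ICC 0.05 row that the real error rate is near 22%. The documents do not support that: it needs 2000 LOAD, which is ADNI's stated maximum rather than the comparison sample, and no shared sites. H2a speaks of matched LOAD participants, and 2000 LOAD would give far more than the stated 90% power.

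A third is that the studies probably share centres: LEADS uses ADNI infrastructure, and Sections 13.2 and 13.3 foresee scanners already qualified for ADNI. Sharing reduces the inflation but largely removes it only if the LOAD sample is drawn in balance from shared centres, which the protocol does not say.

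A fourth is that the remark in 15.2 about differences between sites concerns PET images only, and that the protocol describes central MRI protocols, scanner qualification and rater training. This is fair. It argues for a smaller ICC, especially for imaging, and 15.2 is no evidence of a particular ICC for cognitive scores.

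**Conclusion.** The point holds conditionally. The baseline EOAD-LOAD contrasts under Aims 1 and 2 are specified as linear regression with no allowance for site, and if outcomes differ between sites the standard errors would be too small. At the LOAD number most consistent with the plan's own power statement, the effect ranges from negligible at an ICC of 0.01 to a moderate inflation at 0.05. It grows with the number of LOAD participants used, so drawing on more of ADNI makes the nominal 5% less reliable. The results rest on an assumed ICC, LOAD number, site overlap, SD of 1 and equal site sizes. The documents support neither a single error rate nor a statement that the error is certain. The change is worth making because it is cheap and the affected contrasts are central to both aims.

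**What to change.** In Section 21.1.2, Aims 1 and 2, or in the statistical analysis plan with a reference from there:

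- For the baseline EOAD-LOAD contrasts, keep the covariates and either add a random intercept for enrolling site or use site-cluster-robust standard errors. Use one common code for a centre that takes part in both studies.
- Carry site into the longitudinal mixed models, with participants nested within site.

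In Section 21.1.4, state that the detectable differences for Aims 1 and 2 assume no site clustering, or restate them over a range of ICCs together with the LOAD number assumed.

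The cost is a few sentences and one extra variance term or variance estimator, provided site codes are available in both datasets (assumed here). Confidence intervals will be somewhat wider and, if restated, the detectable differences somewhat larger. Site terms cannot remove a difference common to all of LEADS versus all of ADNI, and reports should say so.

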#### **Aim 2**

MRI and PET based biomarker volumes computed at the mm^3 scale, will be used to assess baseline and longitudinal associations of composite cognitive scores and imaging metrics and identify differences between LEADS EOAD and ADNI LOAD participants. Specifically, multiple linear regression analysis will be used to identify differences between imaging-based metrics in LEADS EOAD vs. ADNI LOAD at baseline and to assess correlations between composite cognitive and imaging measures, while longitudinal data will be analyzed using mixed effects models when data for more than 2 visits per participant is collected. Relevant confounders (e.g. sex, education) will be included as covariates. In addition, summary MRI and PET measures will be analyzed using machine learning techniques to identify a composite metric capturing change across LEADS EOAD participants.

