## 3.0 SCIENTIFIC AIMS

### 3.1 Aim 1

To compare the baseline and longitudinal cognitive and functional characteristics of EOAD compared to LOAD and identify optimal outcome measures for clinical trials.

**H1a:** Controlling for performance on episodic memory tests, EOAD will show greater impairment in executive, language and visuospatial function compared to ADNI LOAD.

**H1b:** EOAD will show more rapid decline on MMSE, ADAS-Cog and CDR-SB compared to ADNI LOAD.

**H1c:** A data-driven analysis of functional ratings and psychometric test scores will identify measures more sensitive to change over time in the full spectrum of EOAD (amnestic and non-amnestic subtypes) than existing composite measures (ADAS-Cog and CDR-SB), leading to a new EOAD composite outcome measure for use in future clinical trials and observational studies.

**Rationale for Aim 1:** Multiple small studies have demonstrated greater impairment in non-memory compared to memory performance[5-7] and more rapid cognitive decline in EOAD than in LOAD[8, 9]. Among these studies the study sample composition (e.g. inclusion of autosomal dominant or focal variants like lvPPA/PCA), assessment and outcome measures vary. Whether clinical trial outcomes employed in LOAD trials (emphasizing episodic memory) should be applied to EOAD or be modified to account for the predominant non-amnestic deficits remains a critical, unanswered question. In this aim we will test both traditional and novel cognitive and functional outcome measures in the full EOAD spectrum defined by current NIA-AA criteria. Our ultimate goal is to empirically reduce our broader battery into a short battery of measures that are especially sensitive in EOAD and feasible for clinical trials.

### 3.2 Aim 2

To compare baseline and longitudinal MRI, amyloid PET, tau PET and CSF and plasma ATN measures between EOAD and LOAD and identify optimal outcome measures for clinical trials.

**H2a:** EOAD will show greater baseline and longitudinal changes in cortical gray matter atrophy and tau burden than matched ADNI LOAD participants, but no differences in baseline or longitudinal amyloid PET, plasma or CSF measures.

**H2b:** Baseline and longitudinal change in cortical tau, gray matter atrophy, CSF and plasma measures will correlate with baseline and longitudinal measures of cognitive function.

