### **8.3 Incomplete Visit Procedures and Protocol Deviations**

All attempts should be made to complete visit procedures as outlined in Appendix 1 within the allowable visit window period. On occasion, a participant might not be able to complete some of the required procedures (i.e., too impaired to complete the full cognitive assessment battery, unable to tolerate the full 60 minute MRI scan protocol, etc.) If a participant is unable to complete the full visit procedure as outlined in Appendix 1, the study team will document the reason for non-completion in the source documents. Participants will be followed as long as they are willing, and every attempt should be made to retain participants for longitudinal follow-up as long as possible. If participants are not willing or able to complete the full schedule of assessments at any visit, those assessments or procedures they are willing to complete should be conducted. It should be emphasized that the major priority

is to keep participants in the study, even if data collection is limited. If participants are no longer willing or able to travel to the clinic for annual visits, as much information should be collected via telephone as long as is possible, see section 8.7. Unless a participant has clearly declined brain autopsy, the neuropathology program should be discussed at each visit. Whenever a study procedure cannot be completed, sites will properly document the reason and review with the study team or IU IRB to determine if a protocol deviation is required.

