#### **8.4 Early Termination Visit**

If a participant wishes to exit the study, an early termination visit will be scheduled (if the participant is willing). This should include as many evaluations as possible, with the exception of PET imaging (see Appendix 1 for visit procedure details). Please contact ATRI Coordinating Center for guidance on what specific procedures should be conducted at an early termination visit.

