## **8.7 Remote Procedures**

Approved visit procedures depicted within the Schedule of Events (Appendix 1) can occur remotely any time it is not possible to conduct the visit in-person due to participant barriers. Remote activities can be conducted via telephone or video bridge. Neuropsychological batteries must be completed via video bridge following the virtual testing procedures manual. Examples of obstacles preventing participants from coming in-person to their visits may include disease progression, or inability to travel for any reason. When possible, participants should still come in-person to complete blood draw, LP, MRI and PET scans as applicable. A combination of remote and in-person data collection is allowed for the same visit. The study team will reassess participant ability to attend in person visits annually. If participants can resume in person visits, they will do so. If not, they will continue remote visit procedures. Prior approval from the IU team is required to conduct fully remote visits and confirmation of method of remote data collection, i.e. via telephone or video must be approved by IU and local regulatory body.

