#### **Aim 2**

We will have 90% power to detect cross-sectional differences in cortical gray matter volumes of at least -0.2. We will have 90% power to detect a cross-sectional difference of  $0.2 \text{ mm}^3$  in flortaucipir SUVR. For longitudinal data, we will have 90% power to detect a difference of -0.001 in annualized Jacobian values between EOAD and LOAD in the region-of-interest. Preliminary longitudinal flortaucipir data in EOAD were too sparse to estimate effect size or power. We will have power of 90% to observe correlations of 0.1 or greater between MRI/ flortaucipir and clinical composite scores - these correlations are considerably lower than the smallest flortaucipir-cognitive correlations observed in our preliminary data.

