## EOAD Participants – Longitudinal Visits

Procedure	Visit	Genetics Status Disclosure	Month 12 a	Month 24 a	Month 36 a	Month 48 / Ongoing Annual Visits a	Annual Neuropath. Phone Check c	Early Termination d
Window Period (days)	See footnote e					+/- 60 b		
Brain donation discussion/provisional consent c,r			X	X	X	X	X	X
Vital Signs			X	X	X	X		X
Neurological and Physical Exams			X	X	X	X		X
Demographics & Medical History r			X	X	X	X		X
Clinical Diagnosis and Clinical Symptom Assessment			X	X	X	X		X
Sex and Reproductive Health Questionnaire r					X o			
Area Deprivation Index Score r					X o			
Concomitant Medications r			X	X	X	X		X
NACC UDS and FTLD Modules, and Neuropsychological Battery f,r			X	X	X	X		X
Amsterdam IADL Questionnaire r			X	X	X	X		X
ADAS-Cog13 r			X	X	X	X		X
Rey Auditory Verbal Learning Test (RAVLT) r			X	X	X	X		X
TabCat: Flanker, Line Length, Line Orientation, and Match			X	X	X	X		X
CDR r			X	X	X	X		X
Pregnancy Test g			X	X	X			
3T MRI/fMRI h			X	X	X			X
Amyloid PET Scan i			X	X	X			
Tau PET Scan i,p,q			X	X	X			
Adverse Event r			X	X	X	X		X
Tau Status Disclosure p,q,r					X p			
Genetic Counseling r,s,t	X							
Study Participation Report j			X	X	X	X		X
Blood for AD blood biomarkers m , DNA, and RNA, PBMC k			X	X	X	X		X
LP Safety Labs (CBC, coagulation profile)			X	X	X			X
Lumbar Puncture (optional) l,m			X	X	X			X
Wellness Check n,r			X	X	X			X

- a) Visit procedures may be split over multiple days without constituting a protocol deviation.
- b) Longitudinal visits should commence within 365 days **+/- 60 days** from the previous visit. However, there must be at least 365 days between the first PET scan of the previous visit and the first PET scan of the next yearly visit. There must also be at least 365 days from second-to-second PET, so that there are no more than two PET scans in a year. FDG PET is not subject to this consideration; it can be the third PET in 365 days. Every attempt should be made to complete longitudinal visits within 60 days.

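### The Aim 2 mixed models are conditioned on more than two visits per participant; applied person by person, this needlessly drops those with one or two imaging visits, mainly for PET

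*Protocol*

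**What the plan says.** Protocol section 21.1.2, Aim 2, plans multiple linear regression for the baseline imaging comparisons. For change over time it says that "longitudinal data will be analyzed using mixed effects models when data for more than 2 visits per participant is collected". It does not say what happens to participants with one or two visits. Aims 1 and 3 in the same section also plan linear mixed models and set no such condition.

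These slopes serve H2a in section 3.2, which expects that "EOAD will show greater baseline and longitudinal changes in cortical gray matter atrophy and tau burden than matched ADNI LOAD participants".

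Other parts of the protocol that bear on the point:

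- **Imaging schedule.** The Appendix 1 schedules place MRI, amyloid PET and tau PET for EOAD at screening/baseline and at Months 12, 24 and 36, so at most four imaging time points. The early termination column of the table "EOAD Participants – Longitudinal Visits" marks MRI but no PET.
- **Early termination, section 8.4.** Of that visit the protocol says "This should include as many evaluations as possible, with the exception of PET imaging".
- **Attendance, section 8.7.** "Examples of obstacles preventing participants from coming in-person to their visits may include disease progression, or inability to travel for any reason". Scans cannot be done remotely, and participants are asked to come in for them when possible.
- **Retention, section 8.3.** "Participants will be followed as long as they are willing", even if data collection is limited.
- **Missing data, section 21.1.3.** Multiple imputation is planned, without detail. No dropout rate is given.

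**The concern.** More than two visits means at least three, and the words about each participant allow an analyst to use this as an entry rule. A linear mixed model needs no such rule. A person with two scans informs the slope directly. A person with one scan informs the intercept and the variance terms and does no harm.

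The rule would also select on retention. An EOAD participant who stops after Month 12 has two PET time points and cannot gain a third, because early termination omits PET. The protocol itself names disease progression as an obstacle to attending in person. If faster decliners stop sooner, those left with three or more scans are on average the slower ones.

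At stake are the EOAD slopes behind H2a and the change-with-change correlations of H2b. Aim 2 also seeks outcome measures for future trials, so an EOAD rate of change that is too slow could carry into their planning.

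**Working it through.** **The plan's own figure.** The only longitudinal power figure for Aim 2 (section 21.1.4) is "a difference of -0.001 in annualized Jacobian values between EOAD and LOAD". It cannot be reproduced, because the standard deviation, the LOAD sample size, the number of visits and the dropout rate are not given. The check is therefore of what the visit condition would do, under assumed values.

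**Inputs.** From the protocol: 650 EOAD and visits at years 0, 1, 2 and 3. Assumed: true mean slope -1.0 per year, between-person slope SD 0.5, intercept SD 1.0, residual SD 0.4, and dropout of 10%, 15% or 25% per year.

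**Precision, with dropout unrelated to decline.** One person's fitted slope has variance 0.5² + 0.4²/S, where S is the sum of squared deviations of that person's visit times.

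- Two visits: S = 0.5, so 0.25 + 0.32 = 0.570
- Three visits: S = 2, so 0.25 + 0.08 = 0.330
- Four visits: S = 5, so 0.25 + 0.032 = 0.282

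A two-visit person therefore carries 0.330/0.570 = 58% of the weight of a three-visit person. At 15% dropout per year the shares with two, three and four visits are 0.85 × 0.15 = 0.1275, 0.85² × 0.15 = 0.108 and 0.85³ = 0.614.

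- Information from all three groups: 0.1275/0.570 + 0.108/0.330 + 0.614/0.282 = 0.224 + 0.328 + 2.178 = 2.730
- Information without the two-visit group: 2.506
- Ratio of standard errors: √(2.730/2.506) = 1.04

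The same steps give 1.03 at 10% and 1.08 at 25%. A full generalized least squares calculation, which also uses the one-visit participants, agrees to two decimals.

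**Bias, by simulation.** Random intercept and slope models were fitted by REML to all participants and to those with at least three visits. Dropout was unrelated to decline, related to the decline observed so far (missing at random, MAR), or related to the true slope (missing not at random, MNAR). The link is in log-odds per SD. Under MAR, loss before Month 12 is unrelated to decline, since no change has yet been observed.

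| Dropout | Per year | Link | Exactly two visits | Slope, all | Slope, three or more |
|---|---|---|---|---|---|
| Unrelated | 10% | 0 | 9% | -1.011 | -1.011 |
| Unrelated | 15% | 0 | 13% | -0.992 | -0.990 |
| MAR | 10% | 0.5 | 11% | -0.999 | -0.973 |
| MAR | 10% | 1.0 | 12% | -1.000 | -0.953 |
| MAR | 15% | 0.5 | 12% | -0.999 | -0.973 |
| MAR | 15% | 1.0 | 17% | -1.001 | -0.934 |
| MAR | 25% | 1.0 | 21% | -1.012 | -0.912 |
| MNAR | 10% | 0.5 | 10% | -0.965 | -0.951 |
| MNAR | 10% | 1.0 | 11% | -0.924 | -0.899 |
| MNAR | 25% | 1.0 | 17% | -0.837 | -0.787 |

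Reading the table against the true slope of -1.0:

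- **Unrelated dropout:** the restriction adds no bias.
- **MAR:** using everyone recovers the slope. The restricted slope is too shallow by 1 - 0.973 = 2.7% to 1 - 0.912 = 8.8%.
- **MNAR:** both are too shallow. The restriction adds 0.965 - 0.951 = 1.4 points to 0.837 - 0.787 = 5.0 points.
- **Number affected:** 0.09 × 650 ≈ 59 to 0.21 × 650 ≈ 137 people have exactly two visits.

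There were three or four replicates per scenario, so the third decimal carries no weight. Both columns come from the same simulated data, so their difference is steadier than either value. The LOAD arm and the H2b correlations were not simulated.

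**The case against.** The sentence does not say that mixed models are used only for people with three visits, and it does not say that anyone is excluded. Section 21.1 plans interim as well as final analyses, and in an annual-visit cohort the early ones would have one or two scans per person. The clause may simply say when the method comes into use, in which case nobody is dropped. Where the protocol does remove participants, in section 21.1.3, it says so. This stands, and it is why the point is conditional. It does not make the wording safe: the threshold is set per participant, and nothing covers two-visit data.

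The protocol also has features that soften the effect. EOAD early termination includes MRI, so someone leaving after Month 12 can still have a third MRI; that stands, and the concern is mainly about PET. Retention is a stated priority. Multiple imputation is planned, but it does not clearly help, because the condition turns on data being collected and imputed visits are not.

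Two stronger readings are tempting. A reader might infer a conflict with the sample-size text because an annualized Jacobian can be obtained from two scans. It can equally come from three or more, so there is no contradiction. A reader might also infer that EOAD progression, and with it the difference from LOAD, will be understated. The documents do not support that as a flat statement: it needs informative dropout, and for the contrast it needs informative loss that differs between cohorts. No figure in the protocol settles either.

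Analysis sets are often left to a SAP. Here, however, the protocol states the condition itself, so it can be corrected there.

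**Conclusion.** The condition is ambiguous and, if applied per participant, an unnecessary restriction, mainly for PET. Under the assumed inputs it would set aside roughly 59 to 137 of 650 EOAD participants with exactly two visits, besides those with one, and widen the standard error of the slope by about 3% to 8% when dropout is unrelated to decline.

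Bias in the EOAD slope is possible but conditional: about 3% to 9% too shallow under the MAR scenarios and none if dropout is unrelated to decline. Under MNAR the restriction adds about 1 to 5 points to a bias that is present anyway. If the same rule is used for ADNI LOAD, the EOAD-LOAD contrast is biased only to the extent that informative loss differs between the studies.

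The direction follows from the protocol's own account of why people stop attending. The sizes rest on assumed variances, dropout rates and link strengths. The point is a modest one and free to correct.

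**What to change.** In section 21.1.2, Aim 2, replace the visit condition with: *Linear mixed models will include every participant with at least one imaging visit, with time as years from the first scan; no minimum number of visits is required.* State that the same rule applies to the ADNI LOAD participants. If a set with at least three visits is wanted, keep it as a sensitivity analysis only.

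The change settles both readings of the present wording. It does not remove bias from MNAR dropout, so a sensitivity analysis for informative dropout is worth considering alongside it.

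The cost is one sentence: no new data, no extra visits and no participants lost.
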